11.2 Sample Size

This study is designed with a primary objective to evaluate the effectiveness of acupuncture versus standard subject management in terms of reduction of neuropathy in actively treated multiple myeloma subjects diagnosed with CIPN. A Fisher's Exact Test with a two-sided alpha = 0.20 significance level will have at least 80% power to detect the difference between a standard of care group proportion of 0.10 and a treatment group proportion of 0.35 when the sample sizes are at least 22 and 44 evaluable subjects, respectively. In order to identify at least 66 evaluable subjects, we anticipate enrolling 75 subjects.

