11.4 Analysis Populations

The intent to treat (ITT) population will consist of all randomized subjects. The ITT population will be used to summarize the CONSORT diagram, subject disposition, and baseline subject disease characteristics. The evaluable population will consist of enrolled subjects who have complete baseline and Week 10 (\pm 1 weeks) neuropathy scores. The evaluable population will be

used for the analyses of all primary and secondary endpoints. Additionally, an intervention-compliant population will be defined as all subjects in the evaluable population who meet all of the following criteria:

- Subjects randomized to the acupuncture arm who have received at least 75%, or 9 of the 12 sessions in up to 13 weeks from randomization.
- Subjects randomized to the control arm who have not received any acupuncture at any time while they are on study.

The intervention-compliant population will be utilized for sensitivity analyses.

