11.5.5 Secondary Analysis

An analysis similar to that described in the primary analysis will be performed for scores obtained at 5 weeks. Additionally, a repeated measures model including a random effect for subject will be estimated for the binary neuropathy improvement score measured at baseline,

week 5 and week 10. Additional baseline factors as previously described above may be added to this model as well.

The secondary endpoint composite measure of specific CIPN symptoms will be treated as a continuous measure and analyzed using analysis of variance techniques. The secondary endpoints measured on a 5-level ordinal scale will be summarized with frequencies and proportions and analysis of variance techniques on the ranks test will be used to test for differences by arm. The number of unhealthy days and activity limitation days will be analyzed using analysis of variance techniques.

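### As placed, the Week 5 comparison and the repeated-measures model fall under a rule requiring a Week 10 score, so observed Week 5 scores of subjects without one go unused

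*Combined protocol and SAP*

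**What the plan says.** Section 11.4 defines the set used for efficacy: "The evaluable population will consist of enrolled subjects who have complete baseline and Week 10" (within one week either side) neuropathy scores. It then assigns that set: "The evaluable population will be used for the analyses of all primary and secondary endpoints". The other two populations do not fill the gap. ITT is confined to the CONSORT diagram, disposition and baseline characteristics. The intervention-compliant set, used for sensitivity analyses, is a subset of the evaluable set.

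Section 11.5.5 plans two further neuropathy analyses. The first: "An analysis similar to that described in the primary analysis will be performed for scores obtained at 5 weeks". The second: "a repeated measures model including a random effect for subject will be estimated for the binary neuropathy improvement score measured at baseline". That model also takes in both later visits. Neither sentence names a population. The list of secondary endpoints in Section 11.3.2 does not include Week 5 neuropathy improvement.

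Midpoint questionnaires are collected in both arms, even when acupuncture sessions are missed or stopped (Sections 5.1, 5.4 and 7.1.2; Section 6, footnote 3). Section 5.2 records reasons for missing questionnaires but gives no rule for using partial follow-up.

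**The concern.** Neither analysis needs every subject to have a Week 10 score. If the Section 11.4 rule governs them, a subject with valid baseline and Week 5 scores who then leaves, or misses the Week 10 assessment, contributes to neither. Two things follow.

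- The Week 5 result compares those who were later measured at Week 10, not those randomized and measured at Week 5. If loss after Week 5 is related to the Week 5 result, and differently by arm, the comparison is distorted.
- The repeated-measures model loses the main reason for fitting it. A correctly specified likelihood model with a subject effect can use incomplete subjects, and it remains valid when dropout depends on the observed Week 5 outcome. Restricted to subjects with a Week 10 score, it loses that protection.

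Both analyses would also carry the same selection as the primary comparison, so neither could show whether that selection mattered.

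**Working it through.** **Inputs (Sections 4.1 and 11.2).** Allocation is 2:1. The test and target are "A Fisher's Exact Test with a two-sided alpha = 0.20 significance level will have at least 80% power", for a "standard of care group proportion of 0.10 and a treatment group proportion of 0.35", when "sample sizes are at least 22 and 44 evaluable subjects, respectively". On enrolment: "In order to identify at least 66 evaluable subjects, we anticipate enrolling 75 subjects".

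**Step 1: reproduce the plan's figures.** Exact enumeration over both binomials was used. The two-sided Fisher p-value sums the tables no more probable than the observed one, and the test rejects at p ≤ 0.20. With 44 and 22 subjects, power is 0.817, which agrees with the stated figure of at least 80%. Planned loss is 75 - 66 = 9, and 9/75 = 12%. At 2:1 this is 50 to 44 (6 lost) on acupuncture and 25 to 22 (3 lost) on control.

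**Step 2: assumptions for the illustration.** The documents give no Week 5 response rates and no timing of losses. Assume that the design rates, 0.35 and 0.10, also hold at Week 5, and that all 9 losses come after a Week 5 score has been obtained. The second assumption gives the largest number of discarded scores under planned enrolment.

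**Step 3: loss unrelated to outcome.** Bias is 0. Using every Week 5 score (50 and 25) gives exact Fisher power of 0.867, against 0.817 with 44 and 22. The cost is 5 percentage points of power.

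**Step 4: loss related to the Week 5 outcome.** If *m* subjects who leave have Week 5 response rate *q*, the rate among those retained shifts by *m*(*p* - *q*)/*n*, where *p* is the true rate and *n* the number retained.

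- Acupuncture, no leaver improved: 6 × 0.35/44 = +0.0477, so 0.35 appears as 0.398.
- Acupuncture, every leaver improved: 6 × (0.35 - 1)/44 = -0.0886, so 0.35 appears as 0.261.
- Control, no leaver improved: 3 × 0.10/22 = +0.0136, so 0.10 appears as 0.114.

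Effect on the true difference of 0.25:

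| Who is lost selectively | Apparent difference | Change relative to 0.25 |
|---|---|---|
| Acupuncture only, all non-responders | 0.398 - 0.100 = 0.298 | +19% |
| Both arms, all non-responders | 0.398 - 0.114 = 0.284 | +14% |
| Control only, all non-responders | 0.350 - 0.114 = 0.236 | -5% |
| Acupuncture only, all responders | 0.261 - 0.100 = 0.161 | -35% |

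Less extreme loss gives less. If 1 of the 6 acupuncture leavers had improved, the shift is 6 × (0.35 - 1/6)/44 = 0.025, or +10%. The shift is linear in *m*, so losses before Week 5 reduce these figures in proportion.

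**Step 5: the repeated-measures outcome.** The outcome is improvement from baseline, analysed at baseline, Week 5 and Week 10. At baseline it is zero for every subject by definition, so that visit carries no outcome information and does not belong in a binary model as a response. The benefit of including incomplete subjects applies to a model for the Week 5 and Week 10 indicators. No bias figure is given for this model, because its odds ratio depends on a specification that the plan does not give.

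**The case against.** Four objections have force.

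1. **The population is inferred.** Section 11.4 speaks of endpoints, and Section 11.3.2 does not list Week 5 improvement as one. A reader might infer that the plan expressly excludes these subjects; it does not say so. The reading rests on where the analyses are placed, on their stated similarity to the primary analysis, and on the absence of any other efficacy population. If that reading is rejected, the two analyses have no defined population, and the same wording is needed.

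2. **Stopping acupuncture is not leaving the study.** A reader might infer that subjects who see no benefit and stop attending drop out of the analysis. Section 8.1 classes them as off treatment, and their questionnaires continue, with mail, electronic and telephone routes available. The point concerns only those who leave the study or miss the Week 10 assessment. That includes control subjects who have acupuncture, whom Section 4.1 discontinues from all further assessments.

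3. **The direction is unknown.** A reader might infer that the rule favours acupuncture, since the trial is unblinded. The documents do not support a sign. The one arm-specific exit that they describe is in the control arm, and the table shows shifts both ways.

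4. **The analyses are supportive.** They carry no stated power or decision rule, and the disposition summary and recorded reasons for missing data will show who left. This limits the weight of the point. It does not justify setting aside scores that the trial has collected.

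**Conclusion.** The point holds in a limited form. Followed as written and placed, the plan leaves observed Week 5 scores out of the Week 5 comparison and the repeated-measures model whenever the Week 10 score is missing, and it conditions the Week 5 comparison on a later event. At most 9 of 75 subjects are affected under planned enrolment. If loss is unrelated to outcome, the cost is power alone, 0.817 against 0.867. If loss is selective, the Week 5 difference moves by +19% to -35% of 0.25 in the one-sided cases worked. These are illustrative ceilings that rest on borrowed Week 5 rates and on all losses falling after Week 5. They are not predictions. Nothing here bears on the primary Fisher test, the sample size or its stated power, and the point is not about how to handle unobserved Week 10 outcomes. Because the remedy is nearly free, the change should be made before analysis.

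**What to change.** Keep the evaluable population for the Week 10 primary Fisher test and, unless otherwise stated, for the other secondary endpoints. Simply confining the Week 10 requirement to the primary comparison would leave the NTX subscale, symptom items and quality-of-life measures with no defined population. Add to Sections 11.4 and 11.5.5:

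> *The Week 5 neuropathy analysis will include all randomized subjects with baseline and Week 5 neuropathy scores, by randomized arm. The repeated-measures model will be fitted by maximum likelihood to the Week 5 and Week 10 improvement indicators in all randomized subjects with a baseline and at least one post-baseline neuropathy score. Baseline is not an outcome in this model, as improvement is zero there by definition; the baseline score may be a covariate.*

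The cost is a few sentences of analysis wording, with no new data, visits or subjects. Denominators will differ between the Week 5, Week 10 and repeated-measures tables, and each table should show its own.

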5.4 Questionnaires

Questionnaires will be administered privately, preferably **prior** to the acupuncture session for those on intervention arm. All subjects will be able to answer the questionnaires via two options: 1) on paper (in person or via certified mail) or 2) via RedCap electronic survey. Phone contact for questionnaires is acceptable if unable to be completed by other stated routes. The form of questionnaire administration will be based on the appointment situation, needs and/ or preference of the subject, and subject access to technology (e.g., computer, tablet, smartphone).

Questionnaires to be completed at Baseline, midpoint and endpoint visits, even if those on the acupuncture arm have not received the acupuncture session on schedule or if sessions are missed.

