6. STUDY CALENDAR

Procedures/Assessments	Screening Visit	Baseline (complete within 2 weeks from consent, can be done at screening AFTER Randomization)	Weeks 1-2 ² : Twice per week	Weeks 3-10 ² : Once per week	Week 5 ± 1 week ^{3,5} Midpoint	Week 10 ± 1 week ^{3,5} Endpoint	Early Termination (if applicable) ⁷	Follow Up (30 days [+7] from last Acup tx)
Informed Consent Form	X							
Randomization via CTMS (within 2 weeks from consent)		X ¹²						
Sociodemographics & Medical History (see 5.3.1 and 5.3.2)		X						
Multiple Myeloma status ⁶		X						
ECOG	X							
Height / Weight/ BMI		X						
Acupuncture Expectancy Scale ⁴		X ⁴						
Acupuncture Treatment ^{1,2}			X ²	X ²				
Collect Chemotherapy regimen information ¹⁰	X					X	X	
Adverse Events of Special Interest ⁸			Continuously, starting at First Acupuncture session			X	X ¹³	
CIPN: Neuropathy 0-10 & neuropathy physical location	X ¹¹				X	X	X	
CIPN: FACT-GOG-NTX		X ¹⁴			X	X	X	
Other Symptoms: Constipation, dizziness, dry mouth		X ¹⁴			X	X	X	
Quality of Life: CDC HRQOL-4		X ¹⁴			X	X	X	
Opioid Intake/ Morphine Equivalent Daily Dose (see Appendix B)		X ⁹			X	X	X	
Concomitant Medication: (See Section 5.3.4 for which medications to collect)		X ⁹			X	X	X	

Key to Footnotes

¹ First acupuncture session to occur within 2 weeks of enrollment (date randomized). Acupuncture treatment schedule to start on a Monday or Thursday only.

² Week 1 for subjects on the acupuncture/intervention arm is the week when the first acupuncture session occurs. Window for acupuncture sessions during Week 1 and Week 2 is at least 1 day (minimum) and no more than 8 days (maximum) between visits. Window for sessions during Weeks 3-10 is at least 2 days (minimum) and no more than 9 days (maximum) between visits. During Week 1 and Week 2, if an acupuncture session is missed, it may be made up the following week (there will be 3 sessions that following week). During Weeks 3-10, no sessions will be made up if missed.

³ Questionnaires at Midpoint and Endpoint should still be collected even if subject decides to discontinue the acupuncture sessions but is willing to stay on study. Week 1 for the control group begins at Randomization.

⁴ Acupuncture Expectancy Scale questionnaire to be collected only from subjects on Intervention (Acupuncture) arm at any time AFTER Randomization has occurred, but PRIOR to first acupuncture session.

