11.3.4 Definition of Exploratory Endpoints

- Opioid use
 - Opioid use assessed through Morphine Equivalent Daily Dose (MEDD) will be calculated for each subject as a quantitative value.
- Concomitant medication use
 - Concomitant medication use assessed through medication name and dose will be determined for each subject.
- Acupuncture administration
 - Acupuncture administration will be defined for each subject on the acupuncture arm as the number of attended acupuncture sessions from 0 to 12.
- Acupuncture expectancy
 - The acupuncture expectancy score will be captured quantitatively for each subject as a composite score ranging from 4 to 20.

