11.5.7 Exploratory Analysis

The exploratory endpoint of Morphine Equivalent Daily Dose (MEDD) will be treated as a continuous measure and analyzed using analysis of variance techniques. Total counts and descriptive statistics of class and dose of concomitant medication use will be summarized by study arm.

In order to evaluate the dose response, dose will be treated as a categorical variable with levels of no acupuncture (0 sessions), low dose (1 – 3 sessions), medium dose (4 – 7 sessions), high dose (8 – 11 sessions) and complete dose (12 sessions). Logistic regression will be performed to investigate the association between dose of acupuncture and CIPN improvement. Acupuncture expectancy will be determined for each subject as a composite measure, which is calculated as the sum of the responses to the four questions on the acupuncture expectancy scale. Logistic regression will be used to evaluate the effect of acupuncture expectancy on the primary endpoint, 2-point improvement in neuropathy.

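### The compliance rule and the dose variable can count acupuncture sessions given after the Week 10 neuropathy score

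*Combined protocol and SAP*

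**What the plan says.** **Compliance.** Section 11.4 requires an acupuncture-arm subject in the evaluable population to have had at least 75% of the sessions, that is "9 of the 12 sessions in up to 13 weeks from randomization". It adds: "The intervention-compliant population will be utilized for sensitivity analyses".

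**Dose.** Section 11.3.4 states: "Acupuncture administration will be defined for each subject on the acupuncture arm as the number of attended acupuncture sessions from 0 to 12". Section 11.5.7 groups this count as 0, 1–3, 4–7, 8–11 and 12 sessions and continues: "Logistic regression will be performed to investigate the association between dose of acupuncture and CIPN improvement". No cut-off date is given.

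**Outcome.** Section 11.3.1 defines the primary endpoint on the change from baseline to the score at Week 10 ± 1 week. Study Calendar footnote 5 runs that clock from the first session in the acupuncture arm, whereas the compliance clock runs from randomization. Footnote 1 allows up to 2 weeks between randomization and the first session.

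**Order of events.** There are two sessions a week in Weeks 1–2 and one a week in Weeks 3–10, so session 12 belongs to Week 10. Section 5.4 wants questionnaires completed "preferably prior to the acupuncture session for those on intervention arm", and wants them completed at the set visits even when sessions are late or missed. Section 7.1.4 allows no make-up sessions in Weeks 3–10 and has session dates recorded.

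**The concern.** An exposure that is meant to explain an outcome should be complete before the outcome is measured. Here the count can include a session that could not have influenced the score. Two analyses use that count: the comparison in the intervention-compliant population, which is the only population section 11.4 names for sensitivity analyses, and the exploratory dose-response model, which addresses a stated objective (section 2.1.4) and a stated expectation (section 1.2).

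There are two consequences. First, the dose received before the outcome is misstated, mainly at the boundary between 11 and 12 sessions. Second, entry to the compliant population can turn on attendance after the subject has reported the outcome. The trial is unblinded and the score is self-reported, so attendance on a later day could depend on how the subject felt. The documents do not determine the direction of any resulting bias.

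**Working it through.** **1. The plan's own figures.**
- Sessions: 2 × 2 + 8 × 1 = 12, and 9/12 = 75%, as section 11.4 states.
- Power: enumerating all tables for the two-sided Fisher exact test (alpha 0.20, 0.10 against 0.35, 22 and 44 subjects) gives 81.7%, which agrees with the stated 80% or more in section 11.2. No session count enters this calculation.

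**2. Where the 13-week limit comes from.** Latest start plus latest score = 2 + 11 = 13 weeks, or 14 + 77 = 91 days. The limit therefore matches the latest permitted score. For a subject who starts on the day of randomization and is scored on day 63, it leaves 91 − 63 = 28 days in which a session would still count.

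**3. Sessions before and after the score.** Take a Monday/Thursday pattern in Weeks 1–2 and weekly sessions after that, in days from the first session: 0, 3, 7, 10, 14, 21, 28, 35, 42, 49, 56, 63. A Thursday start (0, 4, 7, 11, 14, …) gives the same counts.

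| Score taken | Sessions before | On or after |
|---|---|---|
| Day 56, before that day's session | 10 | 2 |
| Day 63, before that day's session | 11 | 1 |
| Day 66 or later | 12 | 0 |

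Which rows apply depends on how Week 10 is read:
- *Calendar weeks.* Footnote 2 makes Week 1 the week of the first session. In seven-day blocks, Week 10 is days 63–69 and Week 9 starts on day 56, so all three rows are possible.
- *Elapsed time.* Footnote 5 can be read as 70 days ± 7, that is days 63–77. Day 56 is then outside the window, and a day-70 score follows all 12 nominal sessions. Post-score sessions arise only for a score early in the window, such as day 63, or when sessions run late.

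**4. Effect on individual subjects.** A full attender scored before the day-63 session has 11 pre-score sessions (the 8–11 level) but is analysed at the 12-session level. That subject is compliant either way. With one post-score session, compliance changes only for a subject with exactly 8 of 11 sessions before the score who then attends session 12.

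**5. How often.** The documents give no attendance rate, so let each session be attended independently with probability q (an assumption), and suppose every subject has one session after the score.
- Compliant only through that session: C(11,8) q⁸ (1−q)³ × q. At q = 0.80 this is 165 × 0.1678 × 0.008 × 0.80 = 0.177.
- Dose level changed by that session: q × [P(0) + P(3) + P(7) + P(11)], where P is the binomial probability of that many sessions out of 11.

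| q | Compliant only through it | Of 44 | Dose level changed |
|---|---|---|---|
| 0.70 | 18.0% | 7.9 | 17.1% |
| 0.80 | 17.7% | 7.8 | 15.7% |
| 0.90 | 6.4% | 2.8 | 29.7% |
| 0.95 | 1.3% | 0.6 | 54.2% |

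The two analyses respond differently. Good attendance nearly removes the compliance problem but enlarges the dose problem, because more subjects sit at the 11/12 boundary.

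With two post-score sessions (a day-56 score, calendar reading only), the compliance shares at 0.80, 0.90 and 0.95 are 41.9%, 23.8% and 8.4%. These are extremes, since they put every subject at the earliest score.

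**The case against.** The case on the other side is substantial.

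- **Elapsed reading.** On that reading a day-70 score follows the whole nominal course, so a post-score session is not shown to be the usual case. Questionnaire-first order is also only a preference. This stands: the problem is conditional. It does not vanish, because day 63 is in the window on either reading and is the nominal day of session 12.
- **The 13-week limit has a rationale.** It does, as step 2 shows. But it fits only the latest permitted score and gives no cut-off for anyone who starts or is scored earlier.
- **The selection argument is modest.** A subject already in clinic for a same-day visit is hardly selected by outcome, and attendance before the score can also depend on response. Both points stand, and counting only pre-score sessions does not cure the second. The stronger ground is the time order itself.
- **Limited reach.** Only a sensitivity population and an exploratory model are involved. This stands.

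A reader might also infer a much longer course from the spacing limits. Footnote 2 says "Window for sessions during Weeks 3-10 is at least 2 days (minimum) and no more than 9 days (maximum) between visits" and allows up to 8 days in Weeks 1–2; chaining the maxima gives 3 × 8 + 8 × 9 = 96 days. The documents do not support this. Sessions are anchored to weeks, with two in each of Weeks 1 and 2 and one in each of Weeks 3–10, and nothing missed in Weeks 3–10 is made up. Sessions on days 0, 8, 16 and 24 would put only one in each of the first two weeks, and the tail would fall after Week 10, where none is scheduled. The gap limits work within the weekly plan and do not extend it.

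**Conclusion.** The point holds in a limited form. As written, the compliance rule and the dose variable can credit sessions given after the outcome: one if the score precedes the day-63 session, two for a day-56 score on the calendar reading, and none if it follows session 12. With one post-score session for everyone and assumed attendance of 0.80, 0.90 or 0.95, about 17.7%, 6.4% or 1.3% of the acupuncture arm would be compliant only because of it. The true share is lower to the extent that subjects are scored after session 12.

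A reader might conclude that the typical subject is misclassified or that the main result is at risk. Neither follows. The first depends on how Week 10 is read and when forms are completed. As for the second, the primary Fisher test uses the evaluable population, which has no session requirement, so its result and power are unchanged. This is a clarification worth making before analysis.

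**What to change.** - **Section 11.4:** replace the limit of 13 weeks from randomization with a requirement that the 9 sessions were received before the subject's Week 10 neuropathy score.
- **Sections 11.3.4 and 11.5.7:** define dose as sessions attended before that score, and redraw the top two levels, for example as 8–10 and 11–12. Under the present levels, the pre-score count would nearly empty the 12-session level, and the timing of the form would decide who is in it. With 11–12 as the top level, a full attender scored just before session 12 stays there. One scored on day 56, with 10 sessions, would not, so the text should also say which reading of Week 10 applies.
- **Data collection:** when form and session fall on the same day, record which came first. For forms not completed in clinic, use the date the subject completed the form.

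**Cost.** Session dates are already recorded (section 7.1.4), so this is a change of wording plus one data item for same-day order. A few subjects may leave the compliant population. Visits, treatment and sample size do not change.
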